## **5.2 AEs coding/grading**

Adverse events (AEs) will be graded according to the CTCAE, Version 4.0. Adverse events will be coded to the preferred term (PT) level using the Medical Dictionary for Regulatory Affairs (MedDRA dictionary).

The CTCAE represents a comprehensive grading system for reporting the acute and late effects of cancer treatments. CTCAE grading is by definition a 5-point scale generally corresponding to mild, moderate, severe, life threatening, and death. This grading system inherently places a value on the importance of an event, although there is not necessarily proportionality among grades (a grade 2 is not necessarily twice as bad as a grade 1). The CTCAE grade of 5 (death) is not used; rather, 'fatal' is collected as AE outcome and death information is also collected on a separate (e)CRF page.

### 5.3 Laboratory parameters derivations

Grade categorization of lab values will be assigned programmatically as per NCI Common Terminology Criteria for Adverse Events(CTCAE) version 4.0. The calculation of CTCAE grades will be based on the observed laboratory values only, clinical assessments will not be taken into account.

For laboratory tests where grades are not defined by CTCAE v4.0, results will be graded by the low/normal/high classifications based on laboratory normal ranges.

A severity grade of 0 will be assigned for all non-missing lab values not graded as 1 or higher. Grade 5 will not be used. For laboratory tests that are graded for both low and high values, summaries will be done separately and labelled by direction, e.g., sodium will be summarized as hyponatremia and hypernatremia.

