### **2.8.3 Laboratory data**

On analyzing laboratory, data from all sources (central and local laboratories) will be combined. The summaries will include all assessments available for the lab parameter collected no later than 30 days after the last study treatment administration date (see Section 2.1.1).

The following summaries will be produced for hematology and biochemistry laboratory data (by laboratory parameter and study part):

- Worst post-baseline CTCAE grade (regardless of baseline status). Each patient will be counted only for the worst grade observed post-baseline.
- Shift tables using CTCAE grades to compare baseline to the worst post-baseline value
- For laboratory tests where CTCAE grades are not defined, shift tables using the low/normal/high classification to compare baseline to the worst post-baseline value.
- Trends of lab parameter values over time (baseline and selected on-treatment time points) should be displayed via boxplots based on time windows and corresponding tables displaying the statistics used for the box plots by the selected time points.

The following listings will be produced for laboratory data:

- Listings of all laboratory data, with CTC grades and classification relative to the laboratory normal range. Lab data collected during the post-treatment period will be flagged.
- Listing of all CTC grade 3 or 4 laboratory toxicities

For laboratory tests (e.g. potassium, sodium, calcium, glucose, magnesium, hemoglobin and lymphocytes) that are graded for both low and high values, summaries will be done separately and labeled by direction, e.g. sodium will be summarized as hyponatremia and hypernatremia.

Unless otherwise specified, the denominator in percentage calculation at each scheduled visit will be based on the number of patients with non-missing value at each particular visit.

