### 5.1.4 Age calculation in Lab data

Following algorithm will be applied to derive the age at each visit in the Lab dataset and will be used in mapping the Lab normal reference ranges per age.

#### Step 1

For screening visit:

Use the age that the site provided in raw data (Age in Days, Age in Months, Age in Years)

Age in month will be age in days/30.4375.

Age in month will floor to integer, for example, if the calculated age in month is 14.3 then the age will be considered as 14 months and will be used when mapping with local reference ranges.

For other visits:

If Age is provided in Days, Age at each visit calculated as [Date of sample Collection(LBDT) - ICF date + Age in Days]

If Age is provided in Months, Age at each visit is calculated as [Date of sample Collection(LBDT) - ICF date + Age in Months + 15 days]

If Age is provided in Years, , Age at each visit is calculated as [Date of sample Collection(LBDT) - ICF date + Age in Years + 6 months].

If age is missing in demo then age in each visit is calculated as [Date of sample Collection(LBDT) - ICF date.

Age in month will be age in days/30.4375.

## Step 2

If reference ranges are not mapped and still missing from Step 1, apply the following rules. If Age is provided in Days, Age at each visit = [Date of sample Collection(LBDT) - ICF date + Age in Days]

If Age is provided in months, Age is [Date of sample Collection(LBDT) - ICF date + Age in Months - 15 days] <= Age at each visit < [Date of sample Collection(LBDT) - ICF date + Age in Months + 15 days]

If Age is provided in years, Age is [Date of sample Collection(LBDT) - ICF date + Age in Months - 6months] <= Age at each visit < [Date of sample Collection(LBDT) - ICF date + Age in Months + 6months]

For both cases above, when there are more than one age ranges, select the ranges in order of (1) lower range (2) upper range. For example, if the age ranges are 13-60 and 61-119, then choose 13-60.

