#### Imputation Rules

CTC grading for blood differentials is based on absolute values. However, this data may not be reported as absolute counts but rather as percentage of WBC.

If laboratory values are provided as '<X' (i.e. below limit of detection) or '>X', prior to conversion of laboratory values to SI unit, these numeric values are set to X.

The following rules will be applied to derive the WBC differential counts when only percentages are available for a xxx differential

$$\text{xxx count} = (\text{WBC count}) * (\text{xxx \%value} / 100)$$

Further derivation of laboratory parameters might be required for CTCAE grading. For instance, corrected calcium can be derived using the reported total calcium value and albumin at the same assessment using the following formula:

$$\text{Corrected Calcium (mg/dL)} = \text{Calcium (mg/dL)} - 0.8 [\text{Albumin (g/dL)} - 4]$$

In order to apply the above formula, albumin values in g/L will be converted to g/dL by multiplying by 0.1, calcium values in mmol/L will be converted to mg/dL by dividing by 0.2495. For calculation of laboratory CTC grades 0 and 1, the normal range for derived corrected calcium is set to the same limits (in mg/dL) as for calcium.

CTC grades for the derived absolute WBC differential counts (neutrophils, lymphocytes) and corrected calcium will be assigned as described above for grading.

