#### Lab normal reference ranges

Local laboratory reference ranges will be collected throughout the study and will be provided by derived age at each visit using the age calculation algorithm provided in Appendix 5.14.

[figure not shown]

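### As worded, the laboratory grading rule gives grade 0 to results that cannot be graded because no reference range was mapped

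*SAP*

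**What the plan says.** Section 5.3 of the SAP has laboratory grades assigned by program under CTCAE version 4.0, from the observed values alone and without clinical judgement. It then states: "A severity grade of 0 will be assigned for all non-missing lab values not graded as 1 or higher". For tests that CTCAE does not grade, it says: "For laboratory tests where grades are not defined by CTCAE v4.0, results will be graded by the low/normal/high classifications based on laboratory normal ranges".

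The ranges come from the sites' laboratories: "Local laboratory reference ranges will be collected throughout the study and will be provided by derived age at each visit". Section 5.1.4 derives that age and provides a second attempt: "If reference ranges are not mapped and still missing from Step 1, apply the following rules". It does not say what happens to a value that still has no range after Step 2.

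The Imputation Rules under section 5.3 tie the lowest grades to a range in the one case they spell out, corrected calcium, which borrows the limits for total calcium: "For calculation of laboratory CTC grades 0 and 1, the normal range for derived corrected calcium is set to the same limits (in mg/dL".

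Section 2.8.3 feeds these grades into two outputs. The first is "Worst post-baseline CTCAE grade (regardless of baseline status", with the rule "Each patient will be counted only for the worst grade observed post-baseline". The second is a shift table from the baseline grade to the worst post-baseline grade.

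**The concern.** Grade 0 should mean that the value was assessed and met no criterion for grade 1 or higher. The sentence in section 5.3 also covers values that could not be assessed. A programmer who follows it has no basis for doing anything but coding them 0, and after that they cannot be told apart from values that were evaluated.

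Two outputs are exposed. After baseline, a patient whose values for a parameter all lack a range appears as grade 0 and stays in the table as a patient without abnormality. At baseline, a false grade 0 makes an abnormality present before treatment look as if it arose on treatment. Laboratory changes are part of the primary endpoint in every part of the study (section 2.5.1), and the cohorts are small, so one or two patients move a percentage visibly.

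**Working it through.** The SAP gives no figure to reproduce, so the check is mainly a reading of its rules in sequence.

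**1. Can a value lack a range?** Yes. Step 2 of section 5.1.4 exists because Step 1 may leave ranges unmapped.

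**2. Does Step 2 close the gap?** Not by its terms.
- Age given in days: at post-screening visits, Step 1 uses collection date minus consent date plus age in days. Step 2 uses the same expression. A value unmapped for that reason at Step 1 stays unmapped.
- Age given in months: Step 2 replaces a single derived age with a window of plus or minus 15 days. This can recover some values.
- Age given in years: Step 2 uses a window of plus or minus 6 months, but the expression refers to age in months, which is not the unit supplied in that branch.
- No branch says what to do after failure.

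**3. Does grading need the range?** For some grades, yes. The corrected-calcium text sets a normal range expressly so that grades 0 and 1 can be calculated. A grade set by a fixed cut-off does not need one and can still be assigned.

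**4. What does the rule do with a value that has no range?** The value is non-missing. Where the criterion for grade 1 or higher needs the missing limit, it cannot be met. Both conditions in section 5.3 are then satisfied, and the value is grade 0.

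**5. Does anything override this?**
- Section 2.8.1 says where adverse events with a missing CTCAE grade are counted. There is no laboratory equivalent.
- Section 2.1 allows a missing category for qualitative data, but a value already set to 0 does not fall into it.
- The denominator rule in section 2.8.3 refers to patients with a non-missing value at each scheduled visit, not a gradable one. It does not expressly cover the worst-grade table.

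**6. Where does it enter the tables?** The worst grade is taken over all post-baseline values, including unscheduled ones (section 2.1.1). The rule therefore changes that table only for patients with no gradable post-baseline value for the parameter. Baseline is more exposed: it is normally the last assessment on or before the start of treatment, so one unmapped value can be enough.

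**7. Illustration.** All counts except the cohort size are assumptions. Section 3 plans at least 10 patients per Part B cohort and at least 10 with LCH in Part D. Let n be the patients with a value, g those at grade 1 or higher, and k those with no gradable post-baseline value, for a parameter whose grades depend on the range.

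- Reported under the rule: g/n
- Among gradable patients: g/(n − k)
- Possible rate over all n: from g/n to (g + k)/n

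| n | g | k | Reported | Among gradable | Possible over all n |
|---|---|---|---|---|---|
| 10 | 3 | 1 | 3/10 = 30% | 3/9 = 33.3% | 30% to 40% |
| 10 | 3 | 2 | 3/10 = 30% | 3/8 = 37.5% | 30% to 50% |

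In the second row the table would show 7/10 = 70% at grade 0, against 5/8 = 62.5% among gradable patients. The reported figure is always the lower bound of what is possible, and nothing in the table shows that any patient could not be graded.

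**The case against.** The best reply is that the sentence was meant only for values that went through grading and came out below grade 1. It follows directly on the statement that grades are assigned by program, and the corrected-calcium text treats grade 0 as something calculated against a range. That may well be the intent, and the SAP nowhere says outright that unmapped values are normal. But the words carry no such condition, and a program is written from the words.

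The plan also works to keep unmapped ranges rare: it collects local ranges throughout, derives age at each visit and has a second step. That stands, and so does the point that one mapped visit gives the patient a post-baseline grade. Section 2.8.3 also lists every result with its grade and its classification against the normal range, so a value without a range should be traceable in the listing. It would not be visible in the tables.

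The consequences are bounded. The analyses are descriptive (section 2.5.2), and a DLT rests on an adverse event that the investigator judges related (section 2.8.1), not on the programmed laboratory grade.

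A reader might infer more than the SAP supports:
- **That severe toxicity is hidden.** The only dependence on a range that the SAP shows for CTCAE grades concerns grades 0 and 1. Nothing in it says that grade 3 needs a reference range in general.
- **That the youngest children are hit hardest.** Ranges are mapped by age, but the SAP does not say where mapping fails.
- **That derived differential counts lack ranges.** The SAP says "The following rules will be applied to derive the WBC differential counts when only percentages are available for a xxx differential" and gives the formula. It does not say whether a range for the absolute count is available.

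**Conclusion.** The point holds as a defect of wording with a definite direction. Followed literally, section 5.3 turns results that cannot be graded for want of a range into grade 0, and nothing else in the SAP prevents it. For range-dependent grades, the effect on the worst-grade table can only be to lower the reported rate of grade 1 or higher. In the shift table, a baseline value treated this way can create an apparent shift from grade 0.

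The size is unknown. The SAP does not say how many values remain without a range after Step 2, and the figures above show only how far one or two such patients would move a cohort of 10. The conclusion assumes that some values stay unmapped and that their grade depends on the missing limit. Grades set by fixed cut-offs are not affected. For tests without CTCAE grades, the SAP does not say how a value without a range is classed, so reporting as normal cannot be asserted there.

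A reader might conclude that the laboratory safety results are materially biased. The SAP does not support that. It supports changing the sentence before the tables are programmed.

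**What to change.** Replace the sentence in section 5.3 with a conditional one: grade 0 is assigned only when the value and every limit needed for grading are available and no criterion for grade 1 or higher is met; otherwise the laboratory grade is missing (not gradable).

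Add to section 2.8.3 that the worst-grade and shift tables show the number of not-gradable patients per parameter, and state which denominator the percentages use. Either choice can be defended. Taking these patients out of the denominator assumes that they resemble the gradable ones; keeping them in gives a lower bound. With the count displayed, a reader can work out both.

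Section 5.1.4 should say that a value still unmapped after Step 2 is passed to this rule.

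The cost is one changed sentence, a cross-reference and one extra table column, with no new data. If patients are excluded, some denominators become smaller. The change does not recover the missing grades; it only stops them from appearing as grade 0.

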#### Imputation Rules

CTC grading for blood differentials is based on absolute values. However, this data may not be reported as absolute counts but rather as percentage of WBC.

If laboratory values are provided as '<X' (i.e. below limit of detection) or '>X', prior to conversion of laboratory values to SI unit, these numeric values are set to X.

The following rules will be applied to derive the WBC differential counts when only percentages are available for a xxx differential

$$\text{xxx count} = (\text{WBC count}) * (\text{xxx \%value} / 100)$$

Further derivation of laboratory parameters might be required for CTCAE grading. For instance, corrected calcium can be derived using the reported total calcium value and albumin at the same assessment using the following formula:

$$\text{Corrected Calcium (mg/dL)} = \text{Calcium (mg/dL)} - 0.8 [\text{Albumin (g/dL)} - 4]$$

In order to apply the above formula, albumin values in g/L will be converted to g/dL by multiplying by 0.1, calcium values in mmol/L will be converted to mg/dL by dividing by 0.2495. For calculation of laboratory CTC grades 0 and 1, the normal range for derived corrected calcium is set to the same limits (in mg/dL) as for calcium.

CTC grades for the derived absolute WBC differential counts (neutrophils, lymphocytes) and corrected calcium will be assigned as described above for grading.

#### Lab normal reference ranges

Local laboratory reference ranges will be collected throughout the study and will be provided by derived age at each visit using the age calculation algorithm provided in Appendix 5.14.

[figure not shown]
## **5.4 Statistical models**

[figure not shown]
### **5.4.1 Primary analysis**

For Part A, Part B, Part C, and Part D there are no formal statistical hypothesis are to be tested. As stated in protocol, the primary focus of the study is to characterize the safety and tolerability of trametinib and to determine the safe and tolerable dose.

### **5.4.2 Key secondary analysis**

There is no key secondary objective.

